## **DESIGN AND OVERVIEW**

This study will employ a single-center double-blind randomized sham-controlled two-parallel-arm design and involve 60 adults with migraine. For each participant, the study will involve 3 study visits and last about 90 days (30 days of the baseline followed by 60 days of the tDCS/sham study intervention). A post-study safety monitoring will continue bi-weekly by phone for 30 days after the last tDCS/sham application.

At Visit 1, patients will provide written informed consent and undergo screening for the eligibility. This will be followed by 30 days of baseline at home during which patients will keep daily records (Daily Diaries) of migraine occurrence and provide answers to a set of symptom-related questionnaires. Patients with 4 or more migraine days per month who fully meet the study eligibility criteria at the end of the baseline period will be randomized in double-blind manner into two groups: Group 1 will be randomized to receive active tDCS in daily 20-minute applications for 60 days; Group 2 will be randomized to receive sham tDCS in daily 20-minute applications for 60 days, self-applied at home. Following randomization, patients will continue keeping the Daily Diaries and Visit #2 will be held either in the patient's home or in the research facility, based on the patient's preference. tDCS device will be deployed to the patient and instructions on tDCS use will be provided. The first tDCS/sham self-application by the patient will be done at Visit 2. Daily tDCS/sham self-application by the patient at home and records in the form of Daily Diaries will continue for the rest of the 60-day period. Study staff will be in regular remote contact with the patient via phone and HIPAA-compliant videoconferencing. Upon conclusion of the intervention, Visit 3 held either in the patient's home or in the research facility, based on the patient's preference. tDCS device will be collected from the patient. Safety monitoring will continue bi-weekly by phone for 30 days after the last tDCS/sham application.

Outcome assessment will be carried out at the end of the baseline, and at the end of month 1 (day  $30\pm 2$ ; the secondary end-point) and month 2 (day  $60\pm 2$ , the primary end-point) of the tDCS/sham intervention.

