### *Outcome Assessment*

Outcome assessment will utilize the following tools:

- Patients's Daily Diaries will be used to take notes of days on which a migraine attack occurs, duration of the attack, severity of migraine pain during the migraine attack, acute antimigraine drug use, and occurrence of any other (non-migraine) headache. Time needed to fill-in the diary is about 1-3 minutes per day (filled-in only on days when headache or migraine medication intake occur).
- Pain Numerical Rating Scale (Pain NRS) is an eleven point [0-10] scale for rating of pain intensity, with the anchor points 0=no pain and 10=worst pain imaginable. Administration time is about 1 minute, rated only on migraine days.

- Migraine-Specific Quality of Life Questionnaire (MSQ) is a validated 25-item questionnaire evaluating impact of migraine on physical, emotional and social component of patients' life. Recall period is four weeks. Administered at the baseline, at the end of month 1 and month 2 of tDCS/sham application. Administration time is about 5 minutes (Rendas-Baum et al., 2013).
- Hamilton Depression Scale (HamD) is a validated 17-item instrument for assessment of depressive symptoms. Administered at the baseline, at the end of month 1 and month 2 of tDCS/sham application. Administration time is about 20 minutes (Hamilton, 1960; Williams, 1988).
- tDCS User Survey is an 8-item questionnaire on user's satisfaction with the use of tDCS. Administered at the end of tDCS use. Administration time is about 5 minutes.
- Occurrence of side effects and adverse events through the study. Tolerability will be determined from occurrence of side effects and adverse events related, probably related or possibly related to tDCS, through the study.

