## **SAMPLE SIZE DETERMNATION AND DATA ANALYSIS**

The sample size calculations are based on responder rates from previous studies of non-invasive neurostimulation in migraine (Lipton et al., 2010; Saper et al., 2011). The numbers used were 15% for sham, based on published trials and 55% for the supraorbital neurostimulation inferred from the pilot study (Gerardy et al., 2009; Lipton et al., 2010; Saper et al., 2011) and 12.1% for sham vs 38.1% for verum in the RCT (Schoenen et al., 2013). To detect a significant difference between the 2 treatments (5% significance level) with an 80% power, the minimum size of each treatment group was estimated at 26 patients, 52 in total who get randomized and initiate the intervention. To account for possible dropouts in the category "randomized, but never started the intervention", we plan to randomize in total 60 patients. To account for patients who do not meet the eligibility criteria at screening, we anticipate we will need to consent about 75 patients.

Statistical analysis will be carried out on an intention-to-treat basis, as well as per protocol for comparison. For Aim 1, the primary comparison will be the between-group comparison at the end of month 2 of the tDCS/sham intervention for the primary and secondary outcomes measures (listed in detail on pgs 7,8). Secondary exploratory comparisons will include between-group comparisons at the month 1 (Day-30) of the 2-month intervention, and within groups comparisons across the study time-points (the baseline, month 1, month 2), as well as comparison of efficacy in patients with chronic and episodic migraines and comparison of efficacy in patient taking abortive migraine medications on 10 or more days with those taking them on 9 or fewer days.

For Aim 2, (Satisfaction with the device and procedure), the primary analysis will include the between-group comparison of at the end of month 2 of the tDCS/sham intervention, evaluating the percentage of patients stating at the end of the trial that they are very satisfied, moderately satisfied, or not satisfied with the device use and procedure, determined from the 8-item tDCS User Survey at the end of the intervention. (We anticipate significant group differences in Survey items pertaining to being more confident in symptom management at home, but no significant group differences in items pertaining to satisfaction with tDCS training and ease of use of the device). In addition, the

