## Analysis Plan (Update 1.29.20)

Participants will be randomized within randomly selected blocks of sizes 2, 4, and 6. The randomization list will be generated by an investigator not otherwise associated with the administration of treatment or collection of data.

All patient characteristics and outcomes will be evaluated for distribution. For all bivariate tests, the appropriate parametric or non-parametric test will be selected based on distribution. Patient characteristics will be described and bivariate tests will evaluate any differences across treatment group (active tDCS vs. sham tDCS). Primary and secondary outcomes at baseline will be described and bivariate tests will evaluate any differences across group. Bivariate tests will evaluate differences in attrition, patient satisfaction, adverse events (including all adverse events, serious adverse events, and adverse events attributed to the treatment), and quality of blinding across group.

All outcomes will be described using data visualization. Differences in outcome between the active tDCS and sham tDCS groups will be evaluated in both intent-to-treat and completer analysis using non-parametric statistics as appropriate (see Table below). Intent-to-treat analysis will impute missing values using all available data. Differences in outcome between people with chronic (15 or more headache days/month) vs. episodic migraine, with and without medication overuse (e.g., using a MSM on 10 or more days per month during the baseline period), and with high and low levels of patient compliance will also be evaluated using the appropriate non-parametric statistic.

Alpha will be set at 0.05, two-tailed, for all analyses. SPSS v. 25.0 and R will be used for all analyses.

Primary Outcome	Description	Tentative Analysis Type
Change in migraine day/30 day	Median change in the number of migraine days per 30 day period, from M0 to M2.	Mann-Whitney U
Secondary Outcomes		
Responders	% of participants who report a 50% reduction in migraine days, from M0 to M2.	Fisher's Exact Test
Change in headache attack/30 days	Median change in number of attacks per 30 day period, from M0 to M2.	Mann-Whitney U
Change in acute medication use	Median change in number of days on which an acute medication was used from M0 to M2.	Mann-Whitney U
Change in headache attack intensity	Median change in NRS from headache days in a 30 day period from M0 to M2.	Mann-Whitney U

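### The primary Mann-Whitney U on change in migraine days is valid but not adjusted for baseline; a pre-specified rank-based ANCOVA is a cheap efficiency improvement whose size (about 0 to 16 power points) rests on assumptions

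*SAP*

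**What the plan says.** The SAP's table describes the primary outcome as "Median change in the number of migraine days per 30 day period, from M0 to M2" and assigns it a Mann-Whitney U test, in a column that calls the choice of analysis tentative. I read M0 as the 30-day baseline and M2 as month 2. The text above the table says that differences between the active and "sham tDCS groups will be evaluated in both intent-to-treat and completer analysis using non-parametric statistics as appropriate (see Table below").

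Baseline values have one other stated use: "Primary and secondary outcomes at baseline will be described and bivariate tests will evaluate any differences across group". Neither document plans a covariate for the primary comparison.

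On allocation, the SAP states: "Participants will be randomized within randomly selected blocks of sizes 2, 4, and 6". The protocol's Randomization paragraph describes blocks of six. The two differ on block size, which is a separate matter, but neither mentions stratification.

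The baseline count exists before allocation. Under Design and Overview, the protocol says that patients who meet the "eligibility criteria at the end of the baseline period will be randomized in double-blind manner into two groups". The Inclusion Criteria set a floor of 4 migraine days, give no upper limit, and admit both episodic and chronic migraine.

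The protocol's outcome is worded as a change in mean days. The SAP's description is a median change, with no between-group difference or interval named.

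**The concern.** Baseline migraine days may vary widely here, from 4 to potentially most of the month. A change score uses baseline with the slope fixed at 1. If patients with high baselines tend to fall further, because the effect is proportional or through regression to the mean, that spread stays in the change scores as noise. A covariate removes it; testing baseline differences between groups does not.

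With 60 patients to be randomised and no stratification described, some sensitivity may be left unused in data already collected. The sample size gives no reassurance on this outcome, because "The sample size calculations are based on responder rates from previous studies of non-invasive neurostimulation in migraine" and not on migraine days.

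**Working it through.** **1. The plan's own figure.** From the protocol: 15% vs 55% responders, two-sided 5%, 80% power. With pooled rate 0.35:

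n = [1.96·√(2·0.35·0.65) + 0.842·√(0.15·0.85 + 0.55·0.45)]² / 0.40² = 21.1.

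With continuity correction: (21.1/4)·[1 + √(1 + 4/(21.1·0.40))]² = 25.9, so 26 per arm. This matches the protocol. The other cited pair, "12.1% for sham vs 38.1% for verum in the RCT", gives 43 per arm uncorrected or 50 corrected, so it is not the source of the 26. Neither calculation concerns migraine days.

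**2. Where a gain comes from.** Let ρ be the correlation between baseline and *change*. Adjusting for baseline multiplies the residual variance of change by 1 − ρ². If M0 and M2 have equal variance and correlation r, then ρ² = (1 − r)/2 and the factor is (1 + r)/2. So the gain depends on how well baseline predicts change; it is zero when ρ = 0.

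**3. Normal model, 26 per arm.** Assumed: r, and an effect giving Mann-Whitney about 67% power, which corresponds to a standardised shift of 1.96 + 0.44 = 2.40. Approximate adjusted power is Φ(2.40/√((1 + r)/2) − 1.96). For r = 0.5: 2.40/√0.75 = 2.77, and Φ(0.81) = 79%.

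| r | Variance factor | Adjusted power, formula | Mann-Whitney, simulated | Rank ANCOVA, simulated | Gain (points) |
|---|---|---|---|---|---|
| 0.3 | 0.65 | 85% | 67.0% | 82.6% | 15.6 |
| 0.5 | 0.75 | 79% | 67.2% | 77.9% | 10.7 |
| 0.7 | 0.85 | 74% | 67.5% | 73.4% | 5.9 |
| 0.8 | 0.90 | 72% | 66.9% | 70.8% | 3.9 |
| 0.9 | 0.95 | 69% | 67.5% | 68.8% | 1.3 |

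At 30 per arm the gains were about 14, 10, 5, 3 and 1 points.

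**4. Day-count models.** Only the responder rates come from the protocol; everything else is assumed. Two sets of models were run. One used skewed counts with baseline between 4 and 30: gain about 0 to 7 points for an additive effect and 5 to 15 for a proportional one. The other mixed episodic and chronic patients, 30 per arm, with no outlying counts:

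- 45% vs 15% proportional reduction: gain 7 to 12 points.
- 35% vs 15%: 6 to 7.
- Fixed difference of 2, 2.5 or 3 days: 2 to 5.5.
- Responder mixture, 55% vs 15%: 6 to 9.
- Responder mixture, 38.1% vs 12.1%: 3 to 4 (Mann-Whitney power 15 to 24%, rank ANCOVA 19 to 28%, with 30% chronic).
- Change unrelated to baseline: -0.4 to +0.2.

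**5. Type I error.** In the mixed-population model at 30 per arm, Mann-Whitney 4.5 to 5.6% and rank ANCOVA 4.5 to 5.8%. Both hold the 5% level closely.

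**6. Why rank-based, and why on change.** The diary is "filled-in only on days when headache or migraine medication intake occur", so a lapse in recording looks like migraine-free days. With 5 to 10% outlying month-2 counts (an assumed rate), rank ANCOVA still gained 1.2 to 11.7 points over Mann-Whitney, while least-squares ANCOVA with robust (HC3) errors ranged from -11.7 to +11.6. Ranking the month-2 count instead of the change lost up to 9 points with outlying counts.

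**7. Test against interval.** With 10% outlying counts, rank ANCOVA was significant while the HC3 interval for the mean difference included zero in 13.4% of trials under a fixed 2.5-day effect, and in 11.7% under 45% vs 15%. A Hodges-Lehmann interval on change goes with the Mann-Whitney test, so it can also disagree with an adjusted test. The share of trials is at least the power gain: at r = 0.5 above, at least 77.9 − 67.2 = 10.7%.

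**The case against.** The strongest reply is that nothing is broken. The Mann-Whitney U is standard, named in advance, consistent with the SAP's median description, and holds its level. Replacing it with a less familiar test is partly preference. That stands, and it is why this is an efficiency point.

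Second, the size cannot be derived from the documents. That stands too. The largest gains need a proportional effect or strong regression to the mean. At the 38.1% vs 12.1% rates, adjustment does not rescue a comparison with low power.

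Third, the protocol limits diary lapses through reminders, weekly submission and regular staff contact, so the 5 to 10% rates may be pessimistic. This weakens the argument against least squares, but rank ANCOVA also gained without lapses whenever baseline predicted change.

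Fourth, chronic-versus-episodic comparisons are already planned. They do not adjust the primary test.

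Fifth, the simulations assume complete data, whereas the SAP's intent-to-treat analysis imputes missing values. The gain under imputation was not examined.

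A reader might infer that the primary test is biased, or that baseline is ignored. The documents do not support either: allocation is randomised, and the change score uses baseline with slope 1. Nor do they support a fixed promised gain, since they give no inputs for one.

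**Conclusion.** The planned test is valid but leaves out an adjustment that would cost little. At 26 to 30 per arm the gain runs from about 0 to 16 power points: larger when baseline predicts change, about 3 to 4 points at 38.1% vs 12.1% without outlying counts, and about zero, at worst about -0.4, when it does not. The range rests on assumed SDs, correlations, effect forms and outlier rates, and on complete data. The direction is well supported for ranked change with ranked baseline, but not for every form of ANCOVA. It would go too far to conclude that the trial's result would be wrong without the change, or that least-squares ANCOVA should decide the primary comparison.

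**What to change.** For the primary outcome only, and before unblinding:

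- Name as the deciding test a rank-based ANCOVA: ranks of M0-to-M2 change (not of the month-2 count) regressed on treatment and ranked baseline days. State how it is applied to imputed data.
- Keep the planned Mann-Whitney U as a sensitivity analysis.
- Report the between-group difference in change with a robust 95% interval, for example Hodges-Lehmann, noting that this one is unadjusted.
- If the ANCOVA-adjusted mean difference is also given, to match the protocol's mean-days outcome, label it as supportive and state that outlying diary counts can make its interval disagree with the rank test.

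The cost is SAP text and one model in software already named (SPSS, R), with no new data, visits or patients. The downsides are one degree of freedom, a less familiar test, a possible loss of about 0.4 points, and possible disagreement between the deciding test and the reported interval.

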**Visit #2 - Familiarization with tDCS and Device Deployment** will be held either at the patient's home or at a designated room at the MJHS Institute, whichever is more convenient for the patient. Familiarization will build on tDCS information provided to the patient via flyer and tDCS booklet prior consenting. The study personnel will demonstrate the equipment and function of the device, instruct the patient on the use of the device, and will review the IRB-approved instructional booklet with the patient. The patient will have an opportunity to experience the sensory sensation associated with tDCS procedure by applying 30 seconds of tDCS stimulation on the arm at the intensity 1.5 mA that is planned be used in the study. The study personnel will also instruct the patient how to establish video connection for a remote contact with the tDCS supervising study personnel located at the MJHS Institute via a HIPAA-compliant Zoom application via the patient's phone, tablet or personal computer. (Patients who do not possess any of these electronic devices will be given an electronic Tablet equipped with Zoom capability for the study duration). At the end of Visit 2, the patient will carry-out the first tDCS/sham application under in-person supervision of study personnel.

**tDCS/Sham Applications in Home Settings.** After the first 20-minute tDCS/sham self-applied by the patient at Visit #2, the tDCS/sham self-applications will continue daily for the total of 60 days. Reminders will be sent by the study personnel via email and text message daily. In addition, study staff will be in regular remote contact with the patient via phone and/or HIPAA-compliant videoconferencing, at least three times per week during the first week and at least twice a week during the remaining weeks.

During the intervention period of the study, patients will continue keeping daily diaries, to document migraine occurrence, related symptoms and medication intake, as done at the baseline period. Patients will receive reminders about the diaries via email and text messages. The diaries will be in electronic form and patients will be sent the diaries to the study site once a week via encrypted HIPAA-compliant email or by fax.

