process data - number of delivered applications and the protocol fidelity in each study group will be analyzed, in order to support evidence on feasibility of the procedure.

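### The one planned comparison of outcome by compliance level uses an undefined split made after randomisation, with no stated arm contrast, so a difference cannot be read as a dose-response.

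*SAP*

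**What the plan says.** The SAP (Analysis Plan, Update 1.29.20) gives the active-versus-sham comparison its own sentence. A later sentence plans further comparisons. It opens with "Differences in outcome between people with chronic (15 or more headache days/month) vs. episodic migraine", goes on to medication overuse during the baseline period, and ends with people "with high and low levels of patient compliance will also be evaluated using the appropriate non-parametric statistic". Alpha is two-tailed 0.05 for every analysis. The SAP does not say what compliance is, where high becomes low, or whether the contrast is pooled over arms, made within one arm, or made between arms at each level.

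The SAP's primary outcome row reads "Median change in the number of migraine days per 30 day period, from M0 to M2". In the protocol (Study Procedures and Methods), "the tDCS/sham self-applications will continue daily for the total of 60 days".

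Other parts of the plan also touch on adherence:
- The protocol (Sample Size and Data Analysis) says that "number of delivered applications and the protocol fidelity in each study group will be analyzed", in support of feasibility.
- The same section says "Statistical analysis will be carried out on an intention-to-treat basis, as well as per protocol for comparison".
- The SAP says that active-versus-sham differences "will be evaluated in both intent-to-treat and completer analysis using non-parametric statistics as appropriate".

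None of these compares outcome across levels of compliance. The protocol's list of secondary exploratory comparisons includes chronic versus episodic migraine and days of abortive medication, but not compliance.

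**The concern.** The other two splits in the sentence describe the patient at entry. Compliance does not: it builds up after allocation, over the same days in which migraine is recorded. Anything that moves both compliance and recorded migraine days produces a high-low gap, whether or not the current does anything. A sham patient who completes every session would count as a high complier, although each sham session gives 30 seconds of current. An open cut-off adds the risk that it is chosen after the data are seen.

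What is at stake is interpretation. The protocol's rationale is that daily home use allows longer courses than the earlier short ones. A significant advantage for high compliers could easily be taken as support for that, and this analysis cannot supply it.

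**Working it through.** **The plan's own figure.** The documents give no figure for the compliance analysis. The one calculation they report is 26 patients per arm (15% versus 55% responders, 5% level, 80% power). It reproduces as a two-sided test with continuity correction:
- Uncorrected: n = [1.96·√(2·0.35·0.65) + 0.842·√(0.15·0.85 + 0.55·0.45)]² / 0.40² = 21.1.
- Corrected: (21.1/4)·[1 + √(1 + 4/(21.1·0.40))]² = 25.9, rounded up to 26.

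The point does not depend on this figure. It uses only the 60 patients to be randomised, about 30 per arm.

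**Timing of the three splits**

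| Split | When it is fixed |
|---|---|
| Chronic or episodic | Migraine type at entry |
| Medication overuse | Baseline period, as the SAP states |
| Compliance | Only during the 60 days after randomisation |

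**Null simulation.** From the plan: n = 60 (pooled) or 30 (one arm), Mann-Whitney U, two-sided 0.05. Assumed: no stimulation effect; bivariate normal compliance and change; correlation ρ between compliance and improvement; change with mean −3 and SD 4 migraine days; median split. Ranges cover separate sets of simulations of 4,000 and 10,000 trials per setting.

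| ρ (assumed) | Significant, n = 60 | Significant, n = 30 |
|---|---|---|
| 0 | about 5% | about 4–5% |
| 0.2 | 21–22% | 11–12% |
| 0.3 | 42–44% | 22–23% |
| 0.4 | 68–70% | 37–38% |

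With the cut at a quarter/three-quarters instead of the median and n = 60, the rates at ρ = 0.2, 0.3 and 0.4 are 19%, 37% and 61%. The inflation does not depend on one choice of cut.

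**Size of the spurious gap.** For a median split the expected difference is 2·√(2/π)·ρ·SD. At ρ = 0.3 and SD 4 this is 2 × 0.798 × 0.3 × 4 = 1.9 migraine days per month in favour of high compliers. The simulation gives the same value.

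**One mechanism that would create a correlation.** Suppose sessions are missed more often on migraine days. With 5% missed on other days and 20%, 30% or 50% on migraine days, the split is significant in 34%, 54% and 73% of null trials at n = 60, and in 20%, 28% and 40% at n = 30. With 10% missed on both kinds of day it is 4.9%. The missing rates and the spread of migraine frequency are assumptions, so this is an illustration only.

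**Contrasts that use randomised arm.** In the same null setting (n = 60, ρ from 0.1 to 0.5), rejection rates are:
- active versus sham by intention to treat: 4.7–5.4%;
- arm-by-compliance interaction: 4.8–5.3%;
- active versus sham within high compliers: 4.6–5.3%.

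The last two hold their level only because compliance was simulated alike in both arms.

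**The case against.** The strongest reply is that the sentence may intend active versus sham within each compliance level. The protocol describes the sibling subgroups as comparisons of efficacy, and that contrast kept its level above. This stands as an ambiguity. The SAP's wording is a contrast between people, with active versus sham dealt with in a separate sentence, so the literal reading is the more natural one. The alternative is safe only if compliance arises alike in both arms.

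It is also fair that every inflated figure rests on an assumed correlation, that at zero there is no inflation, and that a normal model may fit poorly a session count bounded at 60. The comparison touches neither the primary analysis nor a listed secondary outcome.

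Several stronger readings are tempting, and the documents do not support them:
- *This is the only use of delivered dose in the plan.* The protocol also reports delivered applications and fidelity by arm. The per-protocol and completer analyses may also turn on adherence, though neither set is defined.
- *Outcome drives compliance.* Neither document says so. Patients who feel well might stop and those who suffer might persist. Payment depends on following procedures, not on improving, and applies to both arms.
- *Compliance means sessions delivered.* This is an inference. The payment rules join applications, diaries and questionnaires.
- *A false positive is to be expected.* In the correlation model the rate passes 50% only near ρ = 0.4 with all patients pooled, and it is 11–38% within one arm for ρ of 0.2 to 0.4.
- *The plan claims a dose-response.* It does not use the term. The risk lies in how a result would be read.

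The difference between the protocol's per-protocol analysis and the SAP's completer analysis is a separate matter and forms no part of this point.

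**Conclusion.** The concern holds in limited form. The plan has one comparison of outcome across compliance levels. It rests on an undefined split made after randomisation, treated like a baseline subgroup and tested at 0.05, with no arm contrast or exploratory label. Followed literally, it can show a difference with no stimulation effect: about 21%, 43% and 69% of null trials with 60 patients at assumed correlations of 0.2, 0.3 and 0.4, against about 5% at zero. These rates are conditional on correlations that the documents do not give. That the contrast lacks the protection of randomisation does not depend on them. A high-low difference should not be reported as evidence of dose-response. The change is worth making because a foreseeable misreading is cheap to prevent.

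**What to change.** Take compliance out of the SAP's subgroup sentence, and report delivered applications by arm descriptively, as the protocol already intends.

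If an adherence-related effect is wanted, define compliance as delivered sessions, fix any cut-off before unblinding, and use only contrasts based on randomised arm. There are two options:
- **Instrumental-variable (complier) estimate**, with randomised arm as the instrument. With active sessions counted as zero under sham, it is the active-minus-sham difference in mean change divided by the mean number of active sessions delivered in the active arm.
- **Arm-by-compliance contrast**, with the sham high-versus-low result shown beside it as a negative control. A gap in sham like that in active would point away from stimulation as its cause.

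In either case give a confidence interval, label the result exploratory, and state that active versus sham within compliance levels is valid only if compliance arises alike in both arms. A set selected on a minimum number of delivered sessions needs the same caveat, because it too is chosen after randomisation.

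The cost is SAP wording and one exploratory model on data already to be collected. The downside is precision, since any such estimate will be imprecise with 60 patients. As its formula shows, the instrumental estimate largely rescales the intention-to-treat contrast, so it does not itself establish a dose-response.

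### Responder outcome: Boschloo's test would recover power that Fisher's exact test gives up, about 3 to 11 points with equal arms and 0.3 to 5.5 with slightly unequal arms (a cheap improvement, not an error)

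*SAP*

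**What the plan says.** The SAP (Analysis Plan, Update 1.29.20) lists the responder outcome among the secondary outcomes, as the percentage "of participants who report a 50% reduction in migraine days, from M0 to M2". In the column for the tentative analysis type it enters "Fisher's Exact Test". The error level is general: "Alpha will be set at 0.05, two-tailed, for all analyses". On software it says "SPSS v. 25.0 and R will be used for all analyses". Outcomes are to be compared in an intent-to-treat analysis with imputed missing values and in a completer analysis.

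The protocol's primary outcome is change in migraine days, but its section on sample size and data analysis works from responder rates. It gives two pairs: "The numbers used were 15% for sham, based on published trials and 55% for the supraorbital neurostimulation inferred from the pilot study", and "12.1% for sham vs 38.1% for verum in the RCT". The target is "5% significance level) with an 80% power", and the result is that "the minimum size of each treatment group was estimated at 26 patients, 52 in total who get randomized and initiate the intervention". Sixty are to be randomized.

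Neither document mentions that Fisher's test is conservative, and neither names a mid-p or unconditional alternative.

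**The concern.** Fisher's test conditions on the total number of responders as well as on the arm sizes. This design fixes only the arm sizes; the responder total is random. With few patients, conditioning leaves few attainable p-values, so the true type I error can lie well below the nominal 5%, and power is given up with it.

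The responder rate is secondary, but it is the only outcome for which the documents state an assumed effect and a power. In a trial of 60, a choice of test that costs several power points on that outcome deserves a look, particularly if another exact test keeps the same 5% limit and needs no extra patients.

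**Working it through.** **Inputs.** Two-sided 0.05 (SAP). Rates of 15% vs 55% and 12.1% vs 38.1%, 26 per arm as the minimum, and 60 randomized (protocol). The allocation ratio is not stated; 1:1 is assumed, as 26 + 26 = 52 implies, so 60 gives 30 per arm.

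**Step 1: reproduce the protocol's 26.** For 15% vs 55%, the mean rate is 0.35 and the difference is 0.40.

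n = [1.960·√(2·0.35·0.65) + 0.842·√(0.15·0.85 + 0.55·0.45)]² / 0.40² = (1.322 + 0.515)² / 0.16 ≈ 21.1, so 22 per arm.

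With the continuity correction, n′ = (n/4)·[1 + √(1 + 4/(n·0.40))]² = (21.1/4)·(2.214)² ≈ 25.9, so **26 per arm**. This matches the protocol. The same formulas for 12.1% vs 38.1% give 43, or 50 with the correction, so the 26 rests on the first pair alone.

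**Step 2: true size and power by full enumeration.** Let R be the set of 2×2 tables that a test rejects, with x sham and y active responders.

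- Power = Σ over R of Bin(x; n_sham, p_sham)·Bin(y; n_active, p_active).
- Maximum size = the largest value of that sum when both rates equal a common π, over a grid of 4,999 values of π.
- Fisher: R holds the tables with two-sided p ≤ 0.05.
- Boschloo: tables are ordered by the same p-value, and R is the largest set in that order whose maximum size is at most 0.05.

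Fisher's set already has size below 5%, so Boschloo's set contains it. Power therefore cannot fall.

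**Equal arms** (gains from unrounded values):

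| Per arm | Max size, Fisher | Max size, Boschloo | Power, 15% vs 55% | Power, 12.1% vs 38.1% |
|---|---|---|---|---|
| 26 | 2.80% | 4.84% | 82.4% → 88.2% (+5.8) | 46.7% → 57.5% (+10.8) |
| 27 | 2.63% | 4.46% | 83.8% → 88.4% (+4.5) | 48.2% → 59.4% (+11.2) |
| 28 | 2.77% | 4.62% | 85.7% → 89.8% (+4.0) | 50.9% → 61.7% (+10.8) |
| 29 | 2.51% | 4.80% | 86.0% → 91.0% (+5.1) | 52.9% → 63.9% (+11.0) |
| 30 | 2.74% | 4.69% | 87.6% → 91.0% (+3.4) | 55.3% → 59.6% (+4.3) |

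If both arms respond at a documented sham rate, Fisher's size is lower still: 1.0% to 1.5% at 12.1%, and 1.4% to 2.0% at 15%.

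**Slightly unequal arms.** Over all 20 ordered unequal pairs from 26 to 30, Fisher's maximum size is 3.4% to 3.8%, Boschloo's is at most 5.0%, and the gain is 0.3 to 5.5 points. Examples, sham/active:

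| Arms | Max size, Fisher | Power, 15% vs 55% | Power, 12.1% vs 38.1% |
|---|---|---|---|
| 26/27 | 3.6% | 85.2% → 86.9% (+1.7) | 50.1% → 54.8% (+4.7) |
| 27/30 | 3.6% | 87.0% → 90.9% (+3.9) | 58.7% → 64.3% (+5.5) |
| 29/26 | 3.5% | 86.5% → 88.1% (+1.6) | 56.0% → 56.3% (+0.3) |

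**Step 3: does the two-sided definition matter?** A common alternative doubles the smaller one-sided Boschloo p-value. At 12.1% vs 38.1% with arms of 29/31, ordering by the two-sided Fisher p-value gives 64.9% power and doubling gives 61.4%. At 25/27 the figures are 59.5% and 56.8%. The definition therefore has to be written down.

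**The case against.** The case for leaving the row alone has four parts.

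- **Nothing is violated.** A reader might infer from a true size below 3% that the test contradicts the SAP's 0.05. It does not: alpha is an upper limit, and Fisher's test respects it. This stands.
- **Planned power is not lost.** The 26 per arm equals the continuity-corrected result, which approximates Fisher's test, and exact Fisher power at 15% vs 55% is 82.4% against the stated 80%. Sample size and test fit together. At 12.1% vs 38.1% neither test reaches 80% with 26 to 30 per arm, so a reader should not infer that Boschloo rescues that scenario. This stands.
- **The large figures need exactly equal arms.** It is tempting to say that Fisher's size never exceeds 2.8% with 26 to 30 per arm. Every unequal pair in that range exceeds it. Exact equality is also fragile: if 8 of 60 are lost at random from 30/30, the chance of 26/26 is C(30,4)²/C(60,8) ≈ 29%. Single examples are just as delicate. With 3/26 vs 10/26 responders, Fisher gives p = 0.052 and Boschloo p = 0.036, but 3/27 vs 10/26 gives Fisher p = 0.028. This stands and limits the size of the claim.
- **The outcome is secondary and the test is marked tentative.** The primary conclusion does not depend on it. True, but a tentative entry is also easy to revise.

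None of these shows a setting in which Fisher's test does better. In every case computed, Boschloo's test held 5% and had at least equal power.

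**Conclusion.** This is a cheap gain in efficiency on a secondary outcome; the plan contains no error here. Boschloo's test keeps the 5% limit and adds about 3 to 11 power points with equal arms of 26 to 30, or about 0.3 to 5.5 points when the arms differ slightly. If all 60 are analysed as 30/30, the gain is 3.4 points at 15% vs 55% and 4.3 points at 12.1% vs 38.1%. The 11-point gains occur only at the second pair, with equal arms of 26 to 29.

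The figures assume 1:1 allocation, complete binary data, the protocol's rates, and Boschloo's test ordered by the two-sided Fisher p-value. The effect of imputation is not modelled.

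**What to change.** Before unblinding, change the test in the Responders row of the SAP table to: *Boschloo's unconditional exact test, two-sided 0.05, ordered by the two-sided Fisher p-value, with the responder-rate difference and a 95% unconditional exact confidence interval*. Apply it to the observed binary data of the completer analysis. Add a sentence on how the intent-to-treat comparison with imputed values will be tested, because the exact 5% guarantee holds only for complete binary data.

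The cost is one table row and one sentence. The SAP already provides for R, where the test can be run; the code should be checked against the two-sided definition named in the row. The drawbacks are that readers know the test less well than Fisher's, and that the gain is small if the arms end up unequal. The change does not address the low power at 12.1% vs 38.1%, which is a matter of sample size.
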